HIV, Hepatitis B and C testing, as part of the screening assessment, may yield information that we are legally required to disclose to the State of Connecticut and/or CDC as reportable infections. Any identifiable information obtained in connection with this protocol remains confidential. Information is disclosed only with the subject's prior authorization or as required by U.S. and State law. Information that we are legally required to disclose includes abuse of a child or elderly person, or certain reportable infectious disease.

SECTION IX: POTENTIAL BENEFITS

Potential Benefits: Identify any benefits that may be reasonably expected to result from the research, either to the subject(s) or to society at large. (Payment of subjects is not considered a benefit in this context of the risk benefit assessment.)

There is no direct clinical benefit for participating in this study. The present studies may benefit others by providing insight into depression and schizophrenia. It may provide

specific information about the effect of subanesthetic dose of ketamine on the human brain and may provide guidance in further exploring potential mechanisms for the rapid antidepressant effect of ketamine as well as provide potentially important information related to the pathophysiology of psychosis. This information may in turn provide novel diagnostic tests, and may help target new drug development.

The relative risks and inconveniences associated with participation in this study, including ketamine administration, MRS and venipuncture procedures are balanced by the potential benefits to society.

SECTION X: RESEARCH ALTERNATIVES AND ECONOMIC CONSIDERATIONS

1. **Alternatives:** What other alternatives are available to the study subjects outside of the research?

The current study is not for treatment purposes and the subjects do not need to participate.

2. **Payments for Participation (Economic Considerations):** Describe any payments that will be made to subjects, the amount and schedule of payments, and the conditions for receiving this compensation.

All participants will be compensated for their participation. Subjects will be paid \$40 for screening, \$60 for each MRI study (2 studies total), \$40 for each cognitive testing session (2 sessions total), and \$300 for ketamine infusion test day. Failed imaging studies will be repeated and subjects will be paid additionally for the repeated scan. If participation in the scans has already begun and must be cancelled before completion, then compensation will be based on involvement in the study at a rate of \$20 per hour. Reasonable transportation costs up to \$100 on the infusion day will be reimbursed. Receipts must be submitted.

Therefore, we anticipate the subject's total earning – if he/she participates in all sessions – is \$540. At the principal investigator's discretion, further subject payment may be made for travel, parking, lodging, food or transportation.

The debit cards will be offered through the YCCI OnCore ePayments system and will be our preferred payment option. Subjects will be informed that they will receive payment via a Bank of America pre-paid debit card. We will provide their name, address, and telephone number to the Bank of America for processing and their card will be related to their name and number. Their SSN or other information will not be provided. All compensation information will be discussed in the informed consent process.

3. **Costs for Participation (Economic Considerations):** Clearly describe the subject's costs associated with participation in the research, and the interventions or procedures of the study that will be provided at no cost to subjects.

The only costs associated with the study are transportation to and from appointments. All services and evaluations are provided free of charge.

4. **In Case of Injury:** This section is required for any research involving more than minimal risk.
- Will medical treatment be available if research-related injury occurs?
 - Where and from whom may treatment be obtained?
 - Are there any limits to the treatment being provided?
 - Who will pay for this treatment?
 - How will the medical treatment be accessed by subjects?

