C.2. Screening Physical Exam and Laboratories: All subjects will have a standard physical examination at the time of the initial screening. Routine laboratory studies including a complete blood count (CBC) w/ differential, a comprehensive

Table 1. Baseline measures utilized in this study

Baseline Assessments	Medical Assessments	Rating Scales
Demographic Data	Vital signs	BPRS
Psychiatric History	Physical examination	CADSS
Medical History	Mental status exam	PANSS
SCID	Laboratory Assessment	PSQI
MMSE	ECG	PSWQ
		VAS
		Cogstate Cognitive Tasks

Abbreviations: Structured Clinical Interview for DSM IV (SCID), Mini Mental Status Exam (MMSE), Electrocardiogram (ECG), Brief Psychiatric Rating Scale (BPRS), Clinician-Administered Dissociative States Scale (CADSS), Positive and Negative Syndrome Scale (PANSS), Pittsburgh Sleep Quality Index (PSQI), Penn State Worry Questionnaire (PSWQ), VAS (Visual Analog Scale of Mood States).

metabolic panel (e.g., BUN/creatinine, glucose, sodium, potassium, chloride, carbon dioxide, calcium, AST, ALT, fT₄, TSH, bilirubin, total protein, VDRL, vitamin B₁₂, folate, etc.), a complete lipid panel, electrolytes, HIV, hepatitis B and C. A urine sample will be taken and used for a urinalysis drug panel and pregnancy testing. All subjects will also complete an ECG. Care will be taken to exclude pregnant women. All female subjects will have a pregnancy test prior to participating in each MR study.

C.3. Screening Psychiatric Assessments: All subjects will have a psychiatric interview. In addition to the standard psychiatric and mental status examination, subjects will receive a structured diagnostic interview—the Structured Clinical Interview for DSM-IV Disorders (SCID). Baseline and follow-up ratings will also be obtained via assessment measures of depression, anxiety, and adverse effects (see Table 1).

D. Ongoing Clinical Assessments:

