17. *Modified Military Acute Concussion Evaluation (MACE)* - The MACE is a concussion screening tool for the acute assessment of service members involved in a potentially concussive event.
18. *Montgomery-Asberg Depression Rating Scale (MADRS)*: The MADRS is a standardized instrument to ascertain depressed mood and neurovegetative signs and symptoms of depression.
19. *Penn State Worry Questionnaire (PSWQ)*: The PSWQ is a self-report questionnaire to assess for 'worry' symptoms that are typical of generalized anxiety.
20. *Pittsburgh Sleep Quality Index (PSQI)*: The PSQI is a self-report questionnaire to assess sleep quality and sleep disturbance.
21. *Positive and Negative Symptom Scale (PANSS)*: The PANSS is commonly used to measure the severity of symptoms in psychotic disorders. It is a clinician-administered scale and includes three categories of symptoms: (1) positive symptoms, such as hallucination and delusion; (2) negative symptoms, such as flat affect and difficulty in abstract thinking; (3) general psychopathology, such as mannerisms and posturing.
22. *PTSD Checklist (PCL)*: The PCL is used to measure PTSD symptoms and is a self-report questionnaire that has high reliability.
23. *Quick Inventory of Depressive Symptoms – Self-Report (QIDS-SR)*: The QIDS-SR is a patient-rated depression instrument.
24. *Sheehan Disability Scale (SDS)*: The SDS is a brief self-rated measure of disability and impairment.
25. *Beck Suicide Ideation Scale (BSI)*: *The BSI is a 21-item self-report questionnaire that may be used to identify the presence and severity of suicidal ideation. Items on this measure also assess the respondent's suicidal plans, deterrents to suicide, and the level of openness to revealing suicidal thoughts.*
26. *Systematic Assessment for Treatment Emergent Events (SAFTEE)*: The SAFTEE is a commonly used instrument originally developed by NIMH and adapted into a self-report instrument. It examines, in systematic fashion, possible treatment-emergent side effects and probes for specific adverse symptoms, including suicidal thoughts and behaviors, and self-injurious behavior.
27. *Structured Clinical Interview for DSM Disorders (SCID)* will be used to provide current and past diagnoses of psychiatric disorders, notably the inclusion/exclusion criteria of a current major depressive episode.

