28. *Socio-demographic/General Information*: At intake, demographic data and medical history will be assessed with interviews and self-report forms that provide data on age, race, socioeconomic status, marital status, educational and

occupational levels, and significant medical history. These are adapted from previous diagnostic and clinical studies at this center.

D.3. Biochemical Analyses: 10 mL of blood are drawn for the analysis of ketamine levels. Plasma ketamine levels are ascertained via a gas chromatography-mass spectroscopy assay developed by [name] M.D. ⁹⁵.

E. *Lamotrigine Administration:* Subjects randomized to the active lamotrigine group will receive a 300 mg oral dose of the drug 2-hours prior to the start of the ketamine-infusion. Lamotrigine levels will be measured using commercially available radioimmunoassay kits.

A physician who is trained and has experience with lamotrigine and possible allergic and other adverse events will remain in attendance at all sessions that involve drug administration.

F. *Ketamine Administration:* Subjects will complete one test day. Following an overnight fast, IV lines will be inserted into the antecubital vein. They will receive ketamine (0.23mg/kg bolus followed by 0.58mg/kg infusion over approximately 60 minutes).

A physician who is trained and has significant experience with both ketamine and infusion studies will remain in attendance at all sessions that involve ketamine infusion. The subjects will also be attended by a nurse who will accompany them through the study sessions, from the insertion of bilateral cannulae for drug infusion and blood sampling, through to recovery following ketamine infusion.

Baseline Test Session (Test Session 1 Day-0)

- T -15 min: Urine toxicology; Urine pregnancy test (women only);
Breathalyzer; MRI Safety Data Sheet; Metal Detector
- T -0 min: rs-fMRI (and other imaging protocols on the 3T scanner)
- Post fMRI Brief neuropsychological battery

Test session 1 (Day #1)

- T -120 min: Vital signs *; Urine toxicology; Urine pregnancy test (women only); Breathalyzer; PSWQ, PSQI, MRI Safety Data Sheet; Metal Detector; Lamotrigine or matched-placebo control administration
- T-90 min: Intravenous lines started
- T -45 min: MRS setup and baseline scan
- T-0 min: Ketamine infusion begins (0.23mg/kg bolus followed by 0.58mg/kg infused over 60 minutes)
- T 5-75: MRS acquisition continues

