- Blood samples for ketamine, norketamine and lamotrigine levels will be repeated at 15, 30, 60, and 75 minutes **
- T 90: Vital signs, eat a meal, VAS, BPRS, CADSS, PANSS
 - T 300: Participants may be discharged home after being cleared by a study physician.

*Blood pressure, heart rate, and oxygen saturation will be recorded every 10-20 minutes during infusion (T0-75 minutes).

Follow-up After Test Infusion (Day #2)

- T -15 min: Urine toxicology; Urine pregnancy test (women only);
Breathalyzer; MRI Safety Data Sheet; Metal Detector
- T -0 min: rs-fMRI (and other imaging protocols on the 3T scanner)
- Post fMRI Brief neuropsychological battery

Follow-up (1-week, 4-weeks, 8-weeks):

All participants will be contacted by telephone 1-week, 4-weeks, and 8-weeks post-infusion and lamotrigine administration to assess for residual effects of ketamine or lamotrigine and other adverse events (AEs).

Table 2. Schedule of Study Events

Visit	1- Baseline	2-fMRI	3-MRS / Infusion	4-24-hr fMRI
Alcohol & Consumption	x			
BFI	x			
Blood draw/labs	x			
BIS/BAS	x			
BSI		x	x	x
Breathalyzer	x	x	x	x
CADSS			x	
CGI-S/I and PGI-S/I	x			
Collect AEs and SAEs		x	x	x
Cognitive Tasks	Practice	x	x	x
Concomitant Meds	x	x	x	x
C-SSRS	x			
Demographics	x			
ECG	x			
ETI-SR	x			
GPELS	x			
HAM-A	x	x	x	x
*Informed Consent	x			
Ketamine Infusion			x	

KLS	x			
LEC	x			
MADRS	x	x	x	x
M-MACE	x			
MGH-ATRQ	x			
Medical Evaluation	x			
PANSS			x	
PCL	x	x	x	x
PSQI	x	x	x	x
PSWQ	x	x	x	x
QIDS-SR	x	x	x	x
Lamotrigine/Placebo Dose			x	
SAFTEE			x	
SCID-IV	x			
SDS	x			
Serum Pregnancy	x			
Urinalysis	x	x		
Urine Pregnancy		x	x	x
Vital Signs	x		x	

*Informed consent will be obtained prior to any study procedure.

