Ketamine is a dissociative anesthetic that has been used clinically since the late 1960s⁹⁵. Despite extensive experience, there is no clear and compelling evidence of long-term toxicity associated with ketamine administration in medically supervised settings^{97,98}. However, there are acute medical and neuropsychiatric sequelae that deserve special consideration. The ketamine doses employed in the healthy group have been specifically selected to produce mild to moderate behavioral effects without significant sedation. At these doses, ketamine produces a transient alteration of consciousness including altered sensory processing, and thought processes. Initially, subjects frequently feel “drunk” and giddiness is common. As blood levels increase, blood pressure and heart rate increase moderately. This increase is transient and not considered clinically significant. Subjects report differences in complex problem solving evident on frontal lobe and delayed memory tasks, some subjects may report a narrowing of their concentration, feeling distant from surroundings, and enhanced perception of some sensory stimuli. Subjects sometimes report blurred vision and nystagmus. Alterations in the perception of time, body boundaries, and illusions occur. Subjects may experience visual distortions, altered perception of orientation in space, and inability to control thought processes. Subjects may report feeling quite distanced from their surroundings, describe altered awareness of their bodies, and they may close their eyes. During this period, they are still oriented to time and place. They can complete ratings scales testing memory without impairment, their rate of finger tapping is unchanged and the latency of their response on continuous performance tasks of attention is not increased. However, some individuals feel that they cannot control the experience and find it frightening. Vivid dreams and poor sleep quality after infusion of ketamine has also been reported, although dream content was not necessarily unusual and alterations in sleep were not reported on subsequent nights.

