2. results in in-patient hospitalization or prolongation of existing hospitalization
3. results in persistent or significant disability or incapacity
4. results in a congenital anomaly or birth defect OR
5. results in death
6. based upon appropriate medical judgment, may jeopardize the subject's health and may require medical or surgical intervention to prevent one of the other outcomes listed in this definition, or
7. adversely affects the risk/benefit ratio of the study

An adverse event may be graded as severe but still not meet the criteria for a Serious Adverse Event. Similarly, an adverse event may be graded as moderate but still meet the criteria for an SAE. It is important for the PI to consider the grade of the event as well as its "seriousness" when determining whether reporting to the HIC or HSC is necessary.

6. Plan for reporting serious AND unanticipated AND related adverse events anticipated adverse events occurring at a greater frequency than expected, and other unanticipated problems involving risks to subjects or others to the HIC

The investigator will report the following types of adverse events to the HIC:

- a) serious AND unanticipated AND possibly, probably or definitely related events;

b) anticipated adverse events occurring with a greater frequency than expected; and c) other unanticipated problems involving risks to subjects or others.

These adverse events or unanticipated problems involving risks to subjects or others will be reported to the HIC or HSC within 48 hours of it becoming known to the investigator, using the appropriate forms found on the website.

7. Plan for reporting adverse events to co-investigators on the study, funding and regulatory agencies

For the current study, the following individuals, funding, and/or regulatory agencies will be notified:

- All Co-Investigators listed on the protocol.

The principal investigator, [name]., will conduct a review of all adverse events upon completion of every study subject. The principal investigator will evaluate the frequency and severity of the adverse events and determine if modifications to the protocol or consent form are required.

12. Statistical Considerations: Describe the statistical analyses that support the study design.

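### SAFTEE, the only general side-effect checklist, is scheduled at the infusion visit alone and at an unstated time, so it offers no earlier-visit or 24-hour rating for comparison

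*Combined protocol and SAP*

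**What the plan says.** - **The promise.** Section V, 3.C.3 (Screening Psychiatric Assessments) states: "Baseline and follow-up ratings will also be obtained via assessment measures of depression, anxiety, and adverse effects". It then points to Table 1. Table 1 lists no SAFTEE and no other general side-effect checklist.
- **The instrument.** Section V, 3.D.2, item 26 describes SAFTEE as a self-report form: "It examines, in systematic fashion, possible treatment-emergent side effects and probes for specific adverse symptoms". The protocol does not define treatment-emergent or say how SAFTEE items are counted.
- **The schedule.** Table 2 marks SAFTEE at visit 3 (MRS / Infusion) only. A separate row, "Collect AEs and SAEs", is marked at visits 2, 3 and 4, with no method of asking stated. Telephone contacts follow at 1, 4 and 8 weeks, and no instrument is named for them.
- **The infusion-day timeline.** The pre-drug slot at T -120 reads in part: "Breathalyzer; PSWQ, PSQI, MRI Safety Data Sheet; Metal Detector; Lamotrigine or matched-placebo control administration". The slot at T 90 reads: "Vital signs, eat a meal, VAS, BPRS, CADSS, PANSS". Neither names SAFTEE.
- **The use made of event frequency.** The Data and Safety Monitoring Plan, item 6, requires reports of "anticipated adverse events occurring with a greater frequency than expected". Item 7 has the principal investigator review the frequency and severity of adverse events after each subject completes.

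**The concern.** Both groups receive open-label ketamine, so the trial has no ketamine-free control. For any symptom, the natural comparison is the same person before drug. The protocol provides this for mood, anxiety and sleep, whose scales recur from visit 1 to visit 4, but not for the general side-effect form. A fatigue or dizziness item endorsed at visit 3 has no SAFTEE value from an earlier visit to show whether it is new.

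The 24-hour visit has the matching gap. The ketamine risk section warns of effects on the night after dosing: "Vivid dreams and poor sleep quality after infusion of ketamine has also been reported". It also lists nightmares among reported adverse events. Participants may go home at T 300, so a form completed at visit 3 cannot record that night.

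What is at stake is how well the side-effect frequencies can be interpreted, and the monitoring plan asks the investigator to act on those frequencies. The three imaging aims are not affected.

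**Working it through.** The documents give no adverse-event rate, power or precision target tied to SAFTEE, so there is no figure to reproduce. The check is a comparison of sections, followed by one illustration.

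**1. Coverage, read from Table 2 and the call schedule**

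| Contact | SAFTEE | General AE collection |
|---|---|---|
| Visit 1, baseline | no | no |
| Visit 2, fMRI, before drug | no | yes, method unstated |
| Visit 3, infusion | yes, time unstated | yes, method unstated |
| Visit 4, 24 hours | no | yes, method unstated |
| Calls at 1, 4 and 8 weeks | none named | yes, method unstated |

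SAFTEE is scheduled at 0 of 2 visits before the infusion day, 1 of 1 infusion visits and 0 of 1 24-hour visits.

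**2. What one visit-3 administration can show.** If the form is completed before dosing, it records no drug effect. If it is completed after dosing, it has no pre-drug value. If it is completed both before and after dosing that day, which the documents neither state nor exclude, the pre-drug gap closes but the 24-hour gap stays.

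**3. Which effects are covered elsewhere at both times (Table 2)**
- MADRS, QIDS-SR, HAM-A, PSWQ, PCL and PSQI are marked at visits 1, 2, 3 and 4.
- BSI and the cognitive tasks are marked at visits 2, 3 and 4, with cognitive practice at visit 1.
- Mood, anxiety, sleep quality, suicidal ideation and cognition therefore have structured values before drug and at 24 hours.
- From the risks in Section V, 9.A and 9.B, this leaves nausea and vomiting, sedation, hypotension, nightmares and infusion-arm pain for ketamine. For lamotrigine it leaves dizziness, drowsiness, blurred vision, loss of coordination and fatigue. None of these has a dedicated structured measure at 24 hours, and vital signs are not marked at visit 4.

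**4. Illustration of background endorsement.** Let *b* be the prevalence of one symptom in undosed participants. The documents do not give it; I assume 5% to 20%. With no earlier SAFTEE value to subtract, the expected number of endorsements without any drug effect is *N* × *b*, and the chance of at least one is 1 − (1 − *b*)^*N*. *N* is 32 in the Research Plan overview, Statistical Considerations and Targeted Enrollment. Aim 1, Experimental Subjects and Subject Population say 24, so both are shown.

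| *b* (assumed) | Expected, *N* = 32 | Chance of ≥ 1, *N* = 32 | Expected, *N* = 24 | Chance of ≥ 1, *N* = 24 |
|---|---|---|---|---|
| 5% | 32 × 0.05 = 1.6 | 1 − 0.95^32 = 0.81 | 1.2 | 0.71 |
| 10% | 3.2 | 1 − 0.90^32 = 0.97 | 2.4 | 0.92 |
| 20% | 6.4 | 1 − 0.80^32 > 0.99 | 4.8 | > 0.99 |

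With 32 split evenly, the expected count per arm of 16 is 0.8, 1.6 and 3.2. These figures are per symptom. They show that background endorsements are likely to appear; they do not estimate bias.

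**The case against.** The case for leaving the schedule alone has real content.

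- **No counting rule.** A reader might infer that every symptom endorsed on the infusion day becomes a treatment-emergent event. The documents do not say so. Adverse events are also collected at visit 2, before drug, and the investigator attributes each event on a five-level scale that includes unlikely and unrelated. This stands: misattribution is a risk, not a rule of the plan.
- **Overnight effects.** A reader might infer that all of these are left to spontaneous reports. The documents state no elicitation method, and PSQI and HAM-A are marked at visit 4. For poor sleep and anxiety the inference fails. For nightmares and somatic symptoms the method is simply unstated.
- **Timing within visit 3.** One mark need not mean one occasion. Vital signs have a single visit 3 mark but are taken several times that day. A pre-dose SAFTEE at visit 3 therefore cannot be excluded.
- **What 3.C.3 promises.** It does not name SAFTEE. Table 1 lists BPRS, CADSS, PANSS and VAS, which rate ketamine's main acute psychological effects. That reading does not settle the matter: Table 2 marks CADSS and PANSS at visit 3 only and has no row for BPRS or VAS. None of the four is a general side-effect form.
- **Arm comparison.** Randomisation should balance background symptoms on average, so the missing pre-drug rating affects mainly the uncontrolled ketamine frequencies. This stands.
- **Role in the trial.** Statistical Considerations lists no adverse-event outcome and plans no SAFTEE analysis. This stands and limits the weight of the point.

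A reader might also set the chances in the illustration against the 2% of subjects with non-serious reactions cited in Section VI, A.2. That would be wrong. The 2% is a per-subject rate of adverse reactions in a pooled review, not a checklist endorsement rate. At group level it would be 1 − 0.98^32 = 48%.

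**Conclusion.** The point holds in bounded form. SAFTEE is scheduled at one of four visits, with no administration at an earlier visit or at 24 hours and no stated time relative to dosing, although 3.C.3 promises ratings of adverse effects at baseline and follow-up. Because everyone receives ketamine, this schedule gives no sound basis on SAFTEE for separating pre-existing symptoms from ketamine effects. Next-day somatic effects and nightmares depend on adverse-event collection by an unspecified method.

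On the assumed 5% to 20% background prevalence, 1.6 to 6.4 of 32 participants (1.2 to 4.8 of 24) would endorse a given symptom with no drug effect. The finding about the schedule does not depend on that assumption; only the size does. The gap weakens the interpretation of side-effect frequencies that the monitoring plan relies on. It does not threaten the imaging aims, and the documents do not show that adverse events go uncollected at 24 hours.

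**What to change.** 1. Mark SAFTEE in Table 2 at visit 2 (before drug) and visit 4 (24 hours) as well as visit 3.
2. State in the infusion-day timeline when SAFTEE is completed relative to lamotrigine or placebo and to ketamine.
3. Count a SAFTEE symptom as treatment-emergent only if it is new or worse than the pre-drug rating.
4. Tabulate SAFTEE symptoms by arm and by visit.
5. Reconcile Section V, 3.C.3, Table 1 and Table 2 on which adverse-effect measures are given and when.

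Using the same checklist at the 1-, 4- and 8-week calls is optional.

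The cost is an existing self-report form at two visits participants already attend: slightly more participant time and more minor events recorded. The new-or-worse rule removes persistent background symptoms. Visit 2 falls about one week before the infusion, so a symptom that begins in that week would still count as new.
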